#### **iv) Adequacy of protection against risks**

##### **Recruitment and Informed Consent:**

Subjects will be recruited from the UM and VAAAHS Movement Disorders clinics. Individuals willing to participate will be scheduled for the research procedures at which time the nature and risks of the procedures will again be reviewed with the subjects and a written informed consent form will be obtained by one of the study investigators.

One copy of the signed consent form will be given to the subject, one will be placed in the patient's medical record and a third will be kept in the patient's study binder kept at the patient's research site. Study visits will be conducted in the UM Functional Neuroimaging, Cognitive & Mobility Laboratory. Imaging procedures will be performed at the University of Michigan Health System.

##### **Protection Against Risk:**

**Confidentiality of Research Information:** The possibility of unintended disclosure of medical or research data is minimal, but not entirely impossible. We will employ stringent safeguards against unintended and inappropriate discovery and dissemination of personal medical and research data in our subjects by a multi-layered approach. All data bearing potential subject identifiers will reside solely in locked files in the offices of the study

investigators or study coordinator. Original data collection documents will be maintained in secure files under the control of the investigators or study coordinator. Entries regarding details of the research project and its results will not be submitted to clinical medical databases. Electronic databases in the project will employ subject codes that cannot be linked directly to participants without a “key”, possessed only by the study investigators in a secure location, and maintained separately from the databases. Primary databases will not be housed on systems with Internet access, preventing unauthorized intrusions. Personal information that would directly identify study subjects will not be used in any publications or presentations resulting from this research study, unless separate written permission is given by the subject (or proxy). Any superfluous records will be shredded.

Clinical, neuropsychological and Behavioral Testing: Care will be taken to minimize distress. In addition to a lunch and afternoon rest break, subjects are given multiple short breaks during the clinical testing day when needed. Subjects will be addressed in a courteous manner that does not infringe the patient's dignity. Physicians and trained personnel with considerable experience working with older individuals and patients with PD will perform all evaluations and administer tests. These individuals are prepared to respond to patient anxiety, concern and other behavioral changes as appropriate to the situation. Offering breaks and reassuring subjects will further minimize risks when necessary. If needed for some subjects, the clinical testing protocol can be split over 2 days. The UM Functional Neuroimaging, Cognitive and Mobility laboratory has facilities to allow rest breaks when needed. The investigators presently have similar ongoing studies with 1-day clinical testing and 1-day imaging protocols in similar PD populations. Excepts when subjects are severely demented, our PD participants who are typical septuagenarians or octogenarians have no difficulties completing these protocols.

PET Scan & Venipuncture: A nuclear medicine technologist will perform the PET studies under the supervision of a physician who is a specialist in nuclear medicine. A physician or nurse will be available at all times during the study, and any adverse reactions will be treated immediately. A fully equipped medical cart is located in the Nuclear Medicine suite. We will use aseptic techniques and highly trained personnel to minimize the risks associated with venipuncture. No PET studies will be performed on pregnant or potentially pregnant women, as confirmed by pregnancy testing within 48 hours prior to each PET imaging session. In order to lessen the pain and fatigue of lying still, the subject will be given a break outside of the scanner midway through the procedure.

Mood Disorders: All potential participants will be screened formally for mood disorder and suicidal ideation with the Geriatric Depression Scale (GDS) and Columbia Suicide Severity Rating Scale (C-SSRS). Individuals with GDS scores > 5 will be excluded at the discretion of the PI. Similarly, any potential participants describing significant suicidal ideation (scores of 4 or 5 on the relevant questions of the C-SSRS) will be excluded. Mood and suicidality will be evaluated regularly during the study (see Approach; and Schedule of Activities, **Appendix**) with the GDS and C-SSRS. Individuals with worsening GDS scores will be evaluated by the investigators promptly and referred for psychiatric evaluation if clinical interview substantiates concerns about significantly worsening mood disorder. Significant suicidal ideation will result in emergent psychiatric evaluation. VCN administration will be stopped immediately in cases of worsening mood or suicidal ideation. Mood disorder risks will be discussed with potential subjects and the “Black Box” labeling disclosed explicitly. All subjects will be instructed to page the investigators with concerns at any time.

Cardiovascular Disease Events: Individuals with history of stroke (excluded under general exclusion criteria) or myocardial infarction within 1 year, unstable angina, or active PVOD will be excluded. Subjects will be counseled about risk of cardiovascular events and instructed to page the investigators with any concerns. Any suggestions of cardiovascular disease – chest pain, claudication type pain, TIA – will result in VCN discontinuation and emergent evaluation.

Seizures: Individuals with a history of seizures will be excluded. Participants will be counseled about possible seizure risk and instructed to page the investigators with any concerns. Any suggestions of seizures will result in VCN discontinuation and emergent evaluation.

Alcohol Interactions: Individuals with active alcohol abuse will be excluded. The Alcohol Use Disorders Identification Test (AUDIT) will be used to screen for alcohol abuse. Individuals scoring over the recommended cutoffs (>7 for >65 years; >8 for 18-65 years) will be excluded. Participants will be counseled to refrain from alcohol during study participation.

Sleep Disorders: VCN use is associated with sleep disorders, including insomnia and vivid dreams. Participants will be counseled about these potential side effects and instructed to contact the investigators for any concerns.

Gastrointestinal Symptoms: VCN will be initiated at a very low dose and the dose increased over 2-3 days. Individuals who are not able to tolerate the full dose of VCN will be reduced to the next lowest dose as needed. If they are still not able to tolerate the VCN then the VCN will be stopped and the patient will be withdrawn from the study.

Study Monitoring Plan: (please see section vii below).

**v) Potential Benefits of the Proposed Research to the Subjects and Others**

In the course of this study patients will receive clinical evaluations including neuropsychiatric testing and imaging studies. No direct immediate benefit of these studies is anticipated. Although generally the results of these examinations will not be made available to their treating physician, if a significant, unexpected abnormality is detected this will be reported to the patient and his/her physician.

**vi) Importance of the Knowledge to be Gained**

Data obtained from this research may become important for the development of improved methods of reducing gait and balance impairments in PD and other disorders. Such mechanisms would provide a rational basis for targeted intervention of gait and balance impairments in PD and other disorders.

Costs and Payments: Subjects will not be charged for their participation in this study. Subjects will be compensated for time and effort with \$200 for completing the initial clinical evaluations and \$400 upon completion of the imaging or VCN administration procedures. Subjects will receive \$100 to defray housing and meal costs (for subject and caregiver) as we anticipate a number of subjects will have at least one overnight stay, and \$50 to defray travel costs (fuel and parking costs).

**Project III: Inclusion of Women and Minorities**

Inclusion of Women:

Women will be included in this research project. Males and females will be given equal priority in recruitment. However, because PD affects males more than women we expect to recruit a higher percentage of males. The PI will monitor recruitment of women to this project throughout the study, and institute procedures to

enhance the enrollment of women, if numbers are not adequate. See the Targeted/Planned Enrollment Table.

#### Inclusion of Minorities:

See the **Targeted/Planned Enrollment Table** for this project. Enrollment targets are based on population estimates of the 2010 US census for the state of Michigan and Washtenaw County (location of UMHS) with some modifications. For Michigan; 78.9% White, 14.2% African-American, 0.6% Native American, 2.4% Asian, 0% Hawaiian & Pacific Islander, 1.5% Other Race, 2.3% Two or More Races; 4.4% Hispanic/Latino, 95.6% Not Hispanic or Latino. For Washtenaw County; 74.5% White, 12.7% African-American, 0.3% Native American, 7.8% Asian, 0% Hawaiian & Pacific Islander, 1.5% Other Race, 2.3% Two or More Races; 4.0% Hispanic/Latino, 96% Not Hispanic or Latino. Hispanic/Latino residents tend to be recent immigrants and younger than the population average, so we project enrollment of fewer Hispanic/Latino participants than the Hispanic/Latino proportion of state/county population. Similar considerations apply to Asians. Some epidemiologic evidence suggests that PD is less prevalent among African-Americans, so we project fewer African-American enrollees than the proportion of African-Americans in our state/county. The Education and Outreach Core will assist with Minority recruitment.

#### **Project III: Inclusion of Children**

#### Justification for Exclusion of Children:

No children will be included. PD occurs predominantly in late-life and, indeed, the risk of developing PD increases with increasing age. In rare cases with clear familial inheritance, the onset of the disease may occur in the 30's and 40's, but there is no evidence of clinical PD in children. Therefore, the research topic to be studied is not relevant to children.

## Planned Enrollment Report

**Study Title:** Project III: a4b2\* nAChRs, Gait, and Balance in PD

**Domestic/Foreign:** Domestic

**Comments:**

Racial Categories	Ethnic Categories				Total	
	Not Hispanic or Latino		Hispanic or Latino			
	Female	Male	Female	Male		
American Indian/Alaska Native	0	0	0	0	0	
Asian	0	0	0	0	0	
Native Hawaiian or Other Pacific Islander	0	0	0	0	0	
Black or African American	1	0	0	0	1	
White	28	38	1	1	68	
More than One Race	0	0	0	0	0	
Total	29	38	1	1	69	

Study 1 of 1

2.1 Preface

Falls and other abnormalities of gait and balance are common in Parkinson's disease (PD), are largely levodopa unresponsive, and are major contributors to morbidity and mortality. The central theme of the University of Michigan Udall Center is that degeneration of basal forebrain (BF) and pedunculopontine (PPN) cholinergic projections, in the context of degraded striatal motor control, contributes significantly to PD gait and balance deficits. Our preclinical work identifies attentional deficits, secondary to loss of cortical cholinergic afferents, as a key mechanism through which cholinergic deficits contribute to impaired gait and balance. The goal of this pilot target engagement/pharmacodynamic clinical study is to assess $\alpha 4\beta 2^*$ nicotinic cholinergic receptors (nAChRs) as a therapeutic target for improving gait, balance, and attentional capacity in PD.

To demonstrate the $\alpha 4\beta 2^*$ nAChRs are appropriate therapeutic targets in PD, it is necessary to study key pharmacokinetic-pharmacodynamic features of $\alpha 4\beta 2^*$ nAChR in the context of the degenerating, hypocholinergic PD brain, a pathologic environment in which they may exhibit unique features. This personalized medicine approach focuses our studies on hypocholinergic PD subjects. We will assess $\alpha 4\beta 2^*$ nAChR features using Positron Emission Tomography (PET) imaging with the $\alpha 4\beta 2^*$ nAChR ligand [¹⁸F]flubatine, subacute administration of the $\alpha 4\beta 2^*$ nAChR partial agonist varenicline (VCN), and laboratory measures of gait, balance, and attention. We will perform a pharmacodynamics study with subacute VCN administration to determine if $\alpha 4\beta 2^*$ nAChR stimulation improves laboratory measures of gait function, postural control, and attentional function in hypocholinergic PD subjects.

3 Study Objectives and End points

3.1 Study Objectives

Primary Objective

- To use [¹⁸F]flubatine PET to assess varenicline (VCN) occupancy of brain $\alpha 4\beta 2^*$ nAChRs after subacute VCN administration to the subgroup of PD subjects with cholinergic deficits in comparison with normal control subjects.

3.2 End points

All efficacy end points are assessed at the end of treatment (day 10) and at follow-up day 15.

[figure not shown]
3.2.1 Primary Efficacy End points

VCN displacement of thalamic [¹⁸F]Flubatine binding to $\alpha 4\beta 2^*$ nAChRs (the region with the highest [¹⁸F]Flubatine binding). Receptor occupancy is defined as $[(\text{Day 10} - \text{Day 15}) / \text{Day 15}] \times 100\%$.

4 Study Methods

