The recommended clinical VCN dose schedule is 0.5 mg per day for 3 days, followed by 0.5 mg bid for 4 days, followed by 1 mg bid. Mocking et al. recently reported positive neuropsychological results of subacute VCN

**Table 2:** [F]Flubatine binding values for regions expressing high levels of  $\alpha 4\beta 2^*$  nAChRs. N = 3 controls. DVR = Distribution Volume Ratio; SD = Standard Deviation; COV = Coefficient of Variation.

Region	Mean DVR	SD	COV
Thalamus	1.57	0.11	6.9%
Striatum	0.90	0.02	2.1%

treatment (0.5 mg/day for 3 days, then 1 mg/day for 4 days) in normal controls (79). Because we are administering VCN to a clinical population and not young, healthy controls, we propose lower initial doses than Mocking et al. We will start with 0.25 mg/day on a subacute treatment schedule of 10 treatment days. A potential acute side effect of VCN is nausea, though this is unusual in non-smokers with doses below 1 mg per day. To reduce the chance of nausea or other side-effects, we will use a series of escalating dose schedules (**Appendix 2**). VCN will be prepared by the U-M Health System Research Pharmacy. VCN pills are small, easily encapsulated in gelatin capsules, and will be dispensed in blister packs to facilitate administration and compliance monitoring. The initial maximum dose studied will be 0.25 mg/day. Subsequent, projected maximum doses are 0.25 po bid, 0.5 mg po bid, and 1 mg po bid (if needed). Twice daily dosing is used to minimize peak dose effects. We anticipate 3 dose points, each consisting of 3 participants (total of 9

[figure not shown]

Figure 4: Timeline of SA1 Experiment

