participants), to establish the required oral dose for **SA2** and **SA3** experiments. The results of the initial (0.25 mg/day maximum dose) study will be used to select the next dose point. If there is a substantial effect on [F]flubatine binding (>50% reduction), we will use the 0.25 mg bid maximum dose schedule for the next experiment. If the effect on [F]flubatine binding is <50% reduction, we will use 0.5 mg bid maximum dose schedule for the next experiment. Selection of the subsequent dose schedule will be based on the results of the 0.5 mg bid maximum dose experiment. We will increment dose schedules until there is no additional reduction in [F]flubatine binding, i.e., remaining binding is non-specific binding, and the penultimate maximum dose defines our **SA2-SA3** study dose. Based on the work of Lotfipour et al., who found that a single oral 0.5 mg VCN dose produced ~100% receptor occupancy (70), we don't anticipate using the highest (1 mg po bid) dose schedule). We will measure plasma VCN levels at the time of the initial scan (Pharmacokinetics Core, U- M College of Pharmacy; see attached letter from [name], Core Director). These measurements are not for formal PK studies as VCN PK is well established, but rather to confirm study drug compliance. We aim to establish the lowest dose producing high (~100%) receptor occupancy and if we achieve this goal after studying 2 dose schedules (6 participants total), we will stop and proceed to **SA2** experiments.

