### **Standard Methods:**

**MRI and VMAT2 PET Imaging, Standard PET Methods and Image Processing:** See **Clinical Resource Core**. **Flubatine PET Imaging:** [18F]Flubatine will be prepared in high radiochemical purity (>95%) with a method developed by our group (68). PET scans will be acquired using a protocol consisting of 18 frames acquired over 90 min following bolus injections of 8 mCi [F]flubatine. Individual image frames within each scan will be co-registered to frame 10 (10-15 min post-injection) to account for patient motion. Full kinetic modeling requires arterial blood sampling and >two hours of imaging, impractical for this patient population and we will use simpler analyses. Our primary analysis will use an average of the 70-90 min scan data, when tissue TACs are relatively constant, approaching equilibrium (Figure 3). Venous blood samples will be drawn at 70 and 90 min, plasma extracted and counted in a NaI well-counter. Plasma metabolites will be assessed to determine the radioactivity concentration of authentic flubatine. Radiotracer binding measures will be obtained by normalizing the PET tissue concentrations to the authentic venous plasma radiotracer concentration averaged over the 70 and 90 min samples. This measure of tracer binding approximates the total tissue volume of distribution relative to plasma,  $V_T$ . This method is well suited to quantification of flubatine binding as flubatine undergoes minimal catabolism, has only moderate plasma protein binding, and equilibrates instantaneously between blood and plasma (116). A secondary analysis will use the simplified reference tissue model (sRTM) (117). SRTM assumes a reference tissue devoid of specific binding sites, used in lieu of an arterial plasma input function to estimate tissue binding potentials. Since no gray matter tissue is devoid of specific binding sites for flubatine, we will test white matter as a reference tissue. White matter reference regions will be defined on co-registered MR volumes, and segmented with FreeSurfer to produce white matter masks. Binary masks, smoothed to PET resolution with white matter defined by all brain voxels with a mask value >0.9 after smoothing, will assure that reference region voxels have >90% contribution from white matter.

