4.1 General Study Design and Plan

The goal of the first experiment was to select the lowest dose of VCN to produce high (90%) receptor occupancy. $\alpha 4\beta 2^*$ nAChR receptor occupancy is defined as the difference between [¹⁸F]Flubatine binding before and VCN discontinuation, i.e., 10 days after initiation of VCN administration (Day 10) and 5 days after VCN discontinuation (Day 15).

The goal is to have 3/3 subjects achieve >90% receptor occupancy. The dose schedule will be increment, as shown in the figure above, until there is no additional reduction in [18F]Flubatine binding, i.e., remaining binding is non-specific binding, and the penultimate maximum dose will define the dose to be used in the future crossover study.

The second experiment replicates the first experiment in a healthy volunteer population, matched for age. This experiment occurred after the results of the first experiment were known. Thus, only 3 dose groups were assess: 0.25 mg QD, 0.25 mg BID and 0.5 mg BID.

Participants received their first dose of varenicline on Day 1, followed by dose escalations on days 2 and 3 (as needed). On Day 10, they discontinued varenicline and received their first flubatine PET scan. Five days after discontinuation of varenicline (Day 15), they received their second flubatine PET scan.

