4.5 Study Assessments

The primary outcome is $\alpha 4\beta 2^*$ nAChR receptor occupancy, defined as the difference between [¹⁸F]Flubatine binding before and VCN discontinuation, i.e., 10 days after initiation of VCN administration (Day 10) and 5 days after VCN discontinuation (Day 15). Specifically, receptor occupancy is defined as $[(\text{Day 10} - \text{Day 15}) / \text{Day 15}] \times 100\%$.

Adverse events were also collected throughout the 15-day study period.

5 Sample Size

The sample size (planned initially at four PD participants per dosing group) for the VCN- $\alpha 4\beta 2^*$ nAChR occupancy study was based on logistical considerations. The selection of 10 control participants was also based on logistical considerations.

6 General Analysis Considerations

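### The SAP's receptor-occupancy formula has its terms reversed and does not name the binding measure; on the protocol's primary measure (approximately V_T) it would also read too low

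*SAP*

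**What the plan says.** SAP 3.2.1 gives the only primary endpoint: displacement by varenicline of thalamic flubatine binding to the receptor. The formula is: "Receptor occupancy is defined as $[(\text{Day 10} - \text{Day 15}) / \text{Day 15}] \times 100"%. SAP 4.5 gives the same expression, introduced by "Specifically, receptor occupancy is defined as".

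SAP 4.1 fixes what the two days mean: "On Day 10, they discontinued varenicline and received their first flubatine PET scan". The Day 15 scan follows five days off drug. Protocol Specific Aim 1 (Procedures) agrees: the first scan is on the afternoon of day 10, after that morning's dose. The target is also in SAP 4.1: "The goal is to have 3/3 subjects achieve >90% receptor occupancy".

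The SAP names the tracer and the region but not the quantity measured. The protocol (Standard Methods, Flubatine PET Imaging) makes a plasma-normalised late-scan value primary: "This measure of tracer binding approximates the total tissue volume of distribution relative to plasma", V_T. A simplified reference tissue model (SRTM) is secondary. The protocol notes that no gray matter is free of specific sites, so for that model "we will test white matter as a reference tissue".

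Both documents accept that some signal is left when the receptors are saturated. In the protocol's dose-increment rule, the plateau is the point at which "remaining binding is non-specific binding, and the penultimate maximum dose defines our" dose for the later aims. SAP 4.1 has the same rule.

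**The concern.** There are two separate problems.

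The first is the order of the terms. The formula subtracts the larger washout value from the smaller on-drug value, so real occupancy comes out negative.

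The second is the scale. Occupancy is the fraction of specific binding that the drug displaces. V_T contains specific and non-displaceable signal, so dividing by the whole Day 15 value dilutes the result even after the sign is corrected. The SAP neither names a measure that avoids this nor subtracts the non-displaceable part.

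At stake are the occupancies reported by cohort and dose group (SAP 8), which are the whole efficacy result because no test is planned, and the 90% goal in SAP 4.1.

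**Working it through.** **Inputs.** The formula (SAP 3.2.1 and 4.5); Day 10 on drug and Day 15 after washout (SAP 4.1; protocol Specific Aim 1, Procedures); the target of more than 90% (SAP 4.1); V_T as primary measure and SRTM as secondary (protocol, Standard Methods). The plan gives no computed occupancy to reproduce, only the target.

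**Assumptions.** Day 15 is free of drug effect. The non-displaceable part, V_ND, is the same at both scans. The documents do not give f = V_ND/V_T at Day 15, so a range is shown.

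**Step 1: sign, on a purely specific measure.** Let B be binding at Day 15 and Occ the true occupancy. Then Day 10 = B x (1 - Occ), and the formula returns

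[B(1 - Occ) - B]/B = -Occ.

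True occupancies of 50%, 90% and 100% return -50%, -90% and -100%. No degree of displacement gives a positive value.

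**Step 2: scale, on V_T with the sign reversed.** Set V_T at Day 15 to 1. Non-displaceable signal is f and specific signal is 1 - f. Then Day 10 = f + (1 - f)(1 - Occ), and

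(Day 15 - Day 10)/Day 15 = Occ x (1 - f).

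| Assumed f | True 90% reads | Full occupancy reads | True occupancy needed to read 90% |
|---|---|---|---|
| 0.05 | 85.5% | 95% | 0.90/0.95 = 94.7% |
| 0.10 | 81% | 90% | 100% |
| 0.20 | 72% | 80% | not reachable |
| 0.50 | 45% | 50% | not reachable |

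The reading is too low for any f above 0. At f = 0.10 full occupancy reads exactly 90%, so a result above 90% is out of reach from there upward.

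**Step 3: check of the corrected form.** Take f = 0.20 and a true 90%. Day 15 = 1 and Day 10 = 0.20 + 0.80 x 0.10 = 0.28.

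- As printed: (0.28 - 1)/1 = -72%.
- Sign reversed only: (1 - 0.28)/1 = 72%.
- V_ND removed from the denominator: (1 - 0.28)/(1 - 0.20) = 0.72/0.80 = 90%.

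**Step 4: the protocol's 50% cut.** Specific Aim 1 uses a 50% reduction in binding to choose the next dose schedule and does not state the scale. On specific binding it means 50% occupancy. On V_T it means 0.50/(1 - f): 52.6%, 55.6%, 62.5% and 100% at the four assumed values of f. The two scales can therefore describe different results.

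**The case against.** The strongest reply is that the sign is a slip of notation. The SAP calls the endpoint displacement and speaks of a reduction in binding, so the magnitude is clear, and the results are only descriptive, with no test to reverse. That stands as to intent. But the printed definition appears twice and is incompatible with the SAP's own goal, and a primary endpoint should not need repair by its reader.

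The second reply is that SAP 3.2.1 refers to binding to the receptor. Non-displaceable tracer is not bound to it, so specific binding is a fair reading, and the protocol does plan SRTM. This also stands: on a valid binding potential only the sign is wrong. The scale problem is therefore conditional. No sentence says that V_T enters the formula, but none says that it does not, and V_T is the protocol's primary measure.

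Three stronger readings are tempting and are not supported.

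- A reader might infer that the crossover dose would be wrong. The plateau rule asks only whether binding falls further from one dose schedule to the next, so it does not depend on this formula.
- A reader might take f from protocol Table 2, captioned "DVR = Distribution Volume Ratio; SD = Standard Deviation; COV = Coefficient of Variation". The table covers three controls and names no reference region. Its striatal value of 0.90 cannot be a distribution volume ratio against a reference free of specific binding, since 0.90 - 1 = -0.10 would be a negative binding potential. The (1 - f) rule carries over to such a ratio only if the reference has no specific binding. Table 2 therefore gives no usable f.
- A reader might infer that the comparison of PD with controls is biased in a known direction. The documents give f for neither cohort, so neither size nor direction can be stated.

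**Conclusion.** The sign error is certain: it follows from the formula and the scan timing alone, and the goal in SAP 4.1 is unattainable as written. The missing measure is also certain as a gap in the SAP; the protocol does name a primary and a secondary measure, but the SAP does not say which one it uses.

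The understatement is conditional on V_T being used and on V_ND being equal at both scans. Its direction is then certain for any f above 0. Its size is not known: across the assumed range of f, full occupancy reads between 95% and 50%. The effect is confined to the reported occupancies and the 90% goal. The definition should be corrected because it is the trial's only primary endpoint and the correction is cheap.

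**What to change.** In SAP 3.2.1 and 4.5:

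- Define occupancy (%) as 100 x (Day 15 - Day 10)/Day 15, and state that it applies to specific binding.
- Name the measure: the planned SRTM binding potential if the white-matter reference proves valid; otherwise V_T, with occupancy = 100 x (Day 15 - Day 10)/(Day 15 - V_ND) and the method for estimating V_ND stated.
- Apply the 90% goal in SAP 4.1 and the summaries in SAP 8 to that quantity. Report percent change in V_T separately, and do not call it occupancy.
- State which scale the 50% reduction in protocol Specific Aim 1 refers to, so that the protocol and SAP are reconciled.

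The cost is SAP wording and re-analysis of scans already planned, with no new data. The drawback is precision. The protocol names three regions for occupancy and plans three participants per dose point, so an estimated V_ND adds variance, and the white-matter reference is still to be tested. Individual values should therefore be shown on both measures.
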